2.2. Non-target lesions

All other lesions, including pathological lymph nodes, are considered non-target lesions. Measurements of these lesions are not required and these lesions should be followed as “present”, “absent” or “worsening” throughout the study. Multiple non-target lesions involving the same organ can be assessed as a group and recorded as a single item (i.e., multiple liver metastases). Each non-target lesion identified at baseline should be assessed at each subsequent evaluation and be recorded in the eCRF.

Tumor markers will not be used as non-target lesions.

3 Tumor evaluation according to RECIST 1.1

To assess tumor response, the sum of the longest diameters for all target lesions (and short axis for nodal lesions) will be calculated at baseline and throughout the study. At each assessment, response is evaluated first separately for the target lesions and non-target lesions identified at baseline. These evaluations are then used to calculate the overall lesion response considering the target and non-target lesions as well as the presence or absence of new lesions.

3.1 Determination of target lesions response

- **Complete Response (CR):** Disappearance of all target lesions. Any pathological lymph nodes (whether target or non-target) must have reduction in short axis to < 10 mm.
- **Partial Response (PR):** Decrease of at least 30% in the sum of the diameters of target lesions, taking as reference the baseline sum of diameters.
- **Progressive Disease (PD):** Increase of at least 20% in the sum of diameters of target lesions and new lesions, taking as reference the smallest sum on study (including baseline evaluation). In addition to the relative increase of 20%, the sum must also demonstrate an

absolute increase of at least 5 mm. The appearance of one or more new lesions is also considered as progression.

- **Stable Disease (SD):** Neither sufficient shrinkage to qualify for PR nor sufficient increase to qualify for PD.
- **Not Evaluated (NE):** Progression has not been documented and one or more target lesions have not been assessed or have been assessed using a different method than baseline. The only exception is if the SLD of the evaluable target lesions already qualifies for PD. In this case, the Target Response will be PD.

Notes for lymph nodes as target lesions

Lymph nodes identified as target lesions should always have the actual short axis measurement recorded (measured in the same anatomical plane as baseline), even if the nodes regress to below 10mm on study (defined as a normal lymph node). The actual short axis measurement of the nodes is to be included in the sum of target lesions.

This means also that when lymph nodes are included as target lesions, the sum of lesions may not be zero even if CR criteria are met, since a normal lymph node is defined as having a short axis < 10 mm.

Following a CR, a PD can subsequently only be assigned for target lesion response if either a non-nodal lesion reappears or if the absolute sum of the remaining nodal target lesions increases by at least 5mm and at least one of those remaining lesions are at least 10mm in size.

Target lesions that become too small to measure

While on study, all lesions (nodal and non-nodal) recorded at baseline should have their actual measurements recorded at each subsequent evaluation, even very small (e.g., 2 mm). However, if it is the opinion of the radiologist that the lesion has likely disappeared, the measurement should be recorded as 0 mm. If the lesion is believed to be present but too small to measure a default value of 5 mm according to the slice thickness should be assigned. However, if the radiologist is able to provide an actual measure, that should be recorded even if it is below 5 mm.

Lesions that split or coalesce

In some circumstances, disease that is measurable as a target lesion at baseline and appears to be one mass can split and become two or more smaller sub-lesions. When this occurs, the diameters (long axis for non-nodal lesions; short axis for nodal lesions) of the two split lesions should be added together and the sum recorded in the diameter field on the eCRF under the original lesion number. This value will be included in the sum of diameters when deriving target lesion response. The individual split lesions will not be considered as new lesions, and will not automatically trigger a PD designation.

Similarly, as lesions coalesce, a plane between them may be maintained that would aid in obtaining maximal diameter measurements of each individual lesions. If the lesions have truly coalesced such that they are no longer separable, the maximal diameter (long axis for non-nodal lesions; short axis for nodal lesions) for “merged lesion” should be used when calculating the sum of diameters for target lesions. On the eCRF, the diameter of the “merged lesion” should be recorded for the size of one of the original lesions while a size of 0 mm should be entered for the remaining lesion numbers which have coalesced.

Reappearance of lesions

If the lesion appears at the same anatomical location where a target lesion had previously disappeared, it is advised that the time point lesion disappearance be re-evaluated to make sure that the lesion was not actually present and/or not visualized for technical reasons in this previous assessment. If it is not possible to change the 0 value, then the investigator/radiologist has to decide between the following possibilities:

- The lesion is a new lesion, in which case the overall assessment will be considered as PD.
- The lesion is clearly a reappearance of a previously disappeared lesion, in which case the lesion has to be entered in the eCRF with the same numbering as baseline and the tumor assessment will remain based on the sum of tumor measurements as presented above. Proper documentation should be available to support this decision.

For those patients who have only one target lesion at baseline, the reappearance of the target lesion which disappeared previously, even if still small, is considered a PD.

Missing measurements

In cases where measurements are missing for one or more target lesions, it is sometimes still possible to assign PD if the sum of the diameters of the remaining lesions qualifies already for a PD. However, in other cases where a PD cannot definitely be attributed, the target lesion response would be NE.

3.2 Determination of non-target lesions response

- **Complete Response (CR):** Disappearance of all non-target lesions. In addition, all lymph nodes assigned as non-target lesions at baseline must be non-pathological in size (<10mm in short axis).
- **Incomplete Response/Stable Disease (SD):** neither CR nor PD.
- **Progressive disease (PD): Unequivocal progression** of existing non-target lesions.
- **Not All Evaluated (NE):** Progression has not been documented and one or more non-target lesions have not been assessed or have been assessed using a different method than baseline not allowing a reliable comparison.

To achieve “unequivocal progression” on the basis of the non-target disease, there must be an overall level of substantially worsening in non-target disease such that, even in the presence of CR, PR or SD in target disease, the overall tumor burden has increased sufficiently to merit discontinuation of therapy. A “modest” increase in the size of one or more non-target lesions is usually not sufficient to qualify for unequivocal progression status. The designation of progression solely on the basis of change in non-target disease in the face of CR, PR or SD of target disease will therefore be extremely rare.

3.3 New lesions

The appearance of a new lesion is not always associated with PD. A lesion identified on a follow-up assessment in an anatomical location that was not scanned at baseline is also considered a new lesion.

If a new lesion is equivocal, for example because of its small size, continued therapy and follow-up evaluation will clarify if it represents truly new disease. If at the next scheduled assessment, PD is confirmed, the date of progression would be the earlier date when PD was suspected.

3.4 Evaluation of overall lesion response according to RECIST 1.1

The evaluation of overall response at each assessment is a composite of the target lesions response, non-target lesions response and presence of new lesions as shown below.

Overall response by time point (RECIST 1.1)

Target lesions	Non-target lesions	New lesions	Overall response
CR	CR	No	CR ¹
CR	Incomplete response/Stable disease Or not all evaluated (NE)	No	PR
PR	Non-PD or not all evaluated (NE)	No	PR ¹
SD	Non-PD or not all evaluated (NE)	No	SD ^{1, 2}
Not all evaluated (NE)	Non-PD or not all evaluated (NE)	No	Not evaluable ¹ (NE)
PD	Any	Yes or No	PD
Any	PD	Yes or No	PD
Any	Any	Yes	PD

¹ this overall lesion response also applies when there are no non-target lesions identified at baseline.

²once confirmed PR is achieved, all these assessments are considered PR.

If no non-target lesions are identified at baseline, the non-target lesion response at each assessment will be considered “not applicable” (NA).

In some circumstances, it may be difficult to distinguish residual disease from normal tissue. When the evaluation of CR depends on this determination, it is recommended that the residual lesion be investigated (fine needle aspirate / biopsy) to confirm CR. It may be sometimes reasonable to incorporate Fluorodeoxyglucose Positron Emission Tomography (FDG-PET) scanning to complement CT in assessment of progression (especially in case of possible “new” lesion) or in case where a residual radiographic abnormality is thought to represent fibrosis or scarring.

For equivocal findings of PD (e.g., very small and uncertain new lesions, cystic changes or necrosis in existing lesions) treatment may continue until the next scheduled assessment.

3.5 Best overall response according to RECIST 1.1

The best overall response is the best response recorded from the inclusion/ randomization until disease progression/recurrence (taking as reference for PD the smallest sum on study including baseline evaluation).

The best overall response for each patient is determined from the sequence of overall lesion responses by time point according to the following rules:

Best overall response when confirmation of CR and PR required.		
Overall response First Time	Overall response Subsequent time	Best Overall Response
CR	CR	CR
CR	PR	SD, PD or PR ^a
CR	SD	SD provided minimum criteria for SD duration met, otherwise, PD
CR	PD	SD provided minimum criteria for SD duration met, otherwise, PD
CR	NE	SD provided minimum criteria for SD duration met, otherwise NE
PR	PR	PR
PR	CR	PR
PR	SD	SD
PR	PD	SD provided minimum criteria for SD duration met, otherwise, PD
PR	NE	SD provided minimum criteria for SD duration met, otherwise NE
NE	NE	NE

CR = complete response, PR = partial response, SD = stable disease, PD = progressive disease, and NE = inevaluable.

a If a CR is truly met at first time point, then any disease seen at a subsequent time point, even disease meeting PR criteria relative to baseline, makes the disease PD at that point (since disease must have reappeared after CR). Best response would depend on whether minimum duration for SD was met. However, sometimes 'CR' may be claimed when subsequent scans suggest small lesions were likely still present and in fact the patient had PR, not CR at the first time point. Under these circumstances, the original CR should be changed to PR and the best response is PR

- CR: at least two determinations of CR at least 4 weeks apart before progression.
- PR: at least two determinations of PR (or better) at least 4 weeks apart before progression.
- SD: at least one SD assessment (or better) > after a minimum exposure of 5 weeks.

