7.7. Post-study follow-up

PFS-FU visit:

For patients who stopped the study treatment for a reason other than progressive disease based on RECIST 1.1 (e.g., AE), tumor evaluation should be obtained every 6 weeks until disease progression by RECIST 1.1 or for a period of 9 months after the start of study treatment. Beyond 9 months, the evaluations will be performed every 12 weeks until disease progression by RECIST 1.1. Tumor measurements will be recorded in the eCRF with the date and method of tumor assessment and the response evaluation in PFS-FU visit. This follow-up should be done even if patients start subsequent antineoplastic therapies.

Further antineoplastic therapies, given after end of study treatment will be reported in the eCRF with the start date and end date.

Tumor sample on biopsy at the time of progressive disease is to be performed for phase II part 2 in patients with accessible lesions at the time of progressive disease.

OS-FU:

From the safety follow-up or last PFS follow-up visit the patient will be followed for survival every 3 months until death (phone call is considered as a follow-up) or until the date of last contact if the patient is lost to follow-up or withdraws consent for collection of long-term data.

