Therefore, in the calculation of overall response, the methods/modalities listed under the same bullet point will be considered the same:

- ‘CT with contrast’ and ‘CT without contrast’
- ‘Spiral CT with contrast’ and ‘spiral CT without contrast’
- ‘MRI with contrast’, ‘MRI without contrast’, ‘Dynamic contrast – enhanced MRI’ and ‘GD-MRI’

In rare instances when radiological assessment is not possible to determine the progression (e.g., carcinomatous meningitis), other methods may be used (e.g., pathology, cytology).

For patients with a global deterioration of health status requiring discontinuation of study treatment without documented progression, every effort should be made to document objective progression even after discontinuation of treatment.

For phase Ib and phase II part 1 the duration of observation for efficacy lasts from the date of the first study treatment administration to the date of documented progression.

For phase II part 2 the duration of observation for efficacy lasts from the date of randomization to the date of documented progression or death whichever occurs first.

Data of locally performed tumor evaluations will be used for efficacy assessment. For phase II part 2 and to allow independent central review, anonymized copies of CT/MRI will be collected.

To assess objective response, the tumor burden at baseline will be estimated and used for comparison with subsequent measurements. At baseline, tumor lesions will be categorized in target and non-target lesions as described in Appendix IV.

Definitions of measurability of lesions and criteria for response are detailed in Appendix IV. Results for these evaluations will be recorded with as much specificity as possible so that pre- and post-treatment results will provide the best opportunity for evaluating tumor response.

Any CR or PR should be confirmed as described in Appendix IV. In the case of a PR or CR, a confirmatory CT or MRI scan must be done no sooner than 28 days (preferably at the scheduled 6-week interval).

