10.3. Study endpoints

10.3.1. Primary endpoint

Phase Ib: Dose limiting toxicities defined as follows:

- Grade ≥ 3 drug related adverse event. However, fatigue, nausea/vomiting adequately treated with anti-emetics, endocrinopathies adequately controlled with one physiologic hormone replacement, skin toxicity and single laboratory values out of normal range without any clinical correlate, asymptomatic grade ≥ 3 lipase or amylase elevation, tumor flare defined as local pain, irritation, or rash localized at sites of known or suspected tumor or a transient Grade 3 infusion adverse event are excluded
- Liver function test abnormality:
 - o AST or ALT $> 5 \times$ ULN
 - o Total bilirubin $> 3 \times$ ULN
 - o Concurrent AST or ALT $> 3 \times$ ULN and total bilirubin $> 2 \times$ ULN
- Drug related adverse event requiring treatment interruption for more than 2 weeks

The RP2D will be defined as the dose at which less than 33% of the patients (0 or 1 patient among 6 evaluable patients) experience a DLT.

Dose limiting toxicities will be assessed during the first 4 weeks of the combination and will be graded according to NCI CTCAE version 4.03.

To be evaluable for the primary objective of the phase Ib of the study, patients must complete the first 4 weeks of the combination or discontinue before the end of the 4 weeks for a DLT. Patients must receive at least one dose of both IMPs (TG4001 + avelumab) and have at least one valid post-baseline safety assessment. The statement that a patient had no AE, on the Adverse Events eCRF page, constitutes a valid safety assessment. The occurrence of death also constitutes a valid safety assessment. Patients who are not evaluable for phase Ib safety analysis or are withdrawn for other reasons than toxicity, will be replaced.

The DLT population will be the primary population for analyses. These analyses will be repeated on the SAF.

Phase II part 1: The primary endpoint of the phase II part 1 is the Overall Response Rate (ORR by RECIST 1.1 criteria).

The EPP will be the primary population for efficacy analyses in the phase II part 1. These analyses will be repeated on the SAF.

The best response will be recorded from the first study drug administration until documented disease progression. A PR or CR must be confirmed at a subsequent evaluation at least 4 weeks apart.

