10.3.2. Secondary endpoints

The endpoints for secondary objectives of the study are defined as follows:

- Overall Response Rate (ORR) by using RECIST 1.1 (phase Ib, phase II part 2)
- Progression Free Survival (PFS) (phase Ib, Phase II part 1): time from the date of first study treatment administration to the date of first documented tumor progression or death due to any cause, whichever occurs first. If a patient has not had a PFS event at the cut-off date for analysis or at the date when a further antineoplastic therapy (other than those planned as study treatment in the protocol) is started, PFS will be censored at the date of last evaluable tumor assessment before the cut-off or start of further antineoplastic therapy.
- Overall Survival (OS):
- phase Ib and phase II part 1: time from the date of first study treatment administration to the date of death due to any cause. If a patient is not known to have died at the cut-off date for analysis, survival will be censored at the date of last contact.
- Phase II part 2: time from the date of randomization to the date of death due to any cause. If a patient is not known to have died at the cut-off date for analysis, survival will be censored at the date of last contact.
- Duration of overall Response (DoR): applies only to patients whose best overall response is CR or PR. The start date is the date of first documented response (CR or PR) and the end date is the date of first documented disease progression or death, whichever occurs first. If no progression has been observed at the cut-off date of analysis or at the date when a further antineoplastic therapy is started, DoR will be censored at the date of the last evaluable tumor assessment before the cut-off or start of further antineoplastic therapy.
- Disease control rate (DCR): proportion of patients whose best overall response is either CR, PR, or SD.
- Percentage of patients with liver metastases at baseline who have disease progression at D43 (phase II part 2)
- Safety: the assessment of safety of the combination will be based mainly on the frequency of AEs, SAEs, and on the number of laboratory values that fall outside of

predetermined ranges. Other safety data (e.g., ECG, vital signs) will be considered as appropriate.

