10.4.2. Efficacy analyses

The analysis of the efficacy endpoints will be performed on the EPP and repeated on the SAF. The analysis of efficacy will be based on RECIST 1.1.

• Overall Response Rate (ORR)

Overall response rate (ORR) is defined as the proportion of patients whose best overall response is either CR or PR according to RECIST version 1.1. Proportions of patients with a best overall response of CR or PR will be presented along with exact 95% confidence intervals. Patients with best overall response ‘unknown’ will be summarized by reason for having unknown status. Phase II part 2: ORR will be compared between the 2 treatment arms using a (two-sided) 95% CI for the difference in proportion of patients whose best overall response is either CR or PR, stratified by indication using Cochran-Mantel-Haenszel Chi-Square test.

• Progression Free Survival (PFS)

Phase Ib and phase II part 1: PFS (in months) is defined as the time from the date of first study treatment administration to the date of first documented tumor progression or death due to any

cause, whichever occurs first. PFS will be censored if no progression or death is observed at the cut-off date for analysis, or at the date when a further antineoplastic therapy is started. The censoring date will be the date of the last evaluable tumor assessment before the cut-off date or start of further antineoplastic therapy.

Phase II part 2: PFS (in months) is defined as the time from the date of randomization to the date of first documented tumor progression or death due to any cause, whichever occurs first. PFS will be censored if no progression or death is observed at the cut-off date for analysis, or at the date when a further antineoplastic therapy is started. The censoring date will be the date of the last evaluable tumor assessment before the cut-off date or start of further antineoplastic therapy. The primary analysis will be a comparison of PFS between the 2 treatment arms using an unstratified log rank test at the one-sided 5% level in the FAS. A stratified log rank test stratified by indication will be also performed as supportive analysis. [REDACTED]

[REDACTED] HR (together with associated 95% CI) resulting from the stratified and unstratified Cox model will also be presented.

PFS will be presented descriptively using Kaplan-Meier curves. Summary statistics from the Kaplan-Meier distributions will be determined.

- **Duration of Overall Response (in case of CR or PR)**

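### Best overall response does not stop at further antineoplastic therapy, so a confirmed CR or PR reached on post-study treatment counts in ORR

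*Combined protocol and SAP*

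**What the plan says.** **Response window.** Appendix IV, section 3.5: "The best overall response is the best response recorded from the inclusion/ randomization until disease progression/recurrence". Section 10.3.1, for the part 1 primary endpoint: "The best response will be recorded from the first study drug administration until documented disease progression". Section 8: "For phase II part 2 the duration of observation for efficacy lasts from the date of randomization to the date of documented progression or death". Confirmation of a CR or PR in Appendix IV needs two determinations at least 4 weeks apart before progression. New therapy is not mentioned.

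**Endpoints built on it.** Section 10.4.2 defines ORR as the "proportion of patients whose best overall response is either CR or PR according to RECIST version 1.1". DCR adds SD. Neither carries a rule for new therapy. ORR is primary in part 1 and secondary in phase Ib and part 2.

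**Scanning after treatment stops.** Section 7.7, for patients who stopped for a reason other than RECIST progression: "tumor evaluation should be obtained every 6 weeks until disease progression by RECIST 1.1 or for a period of 9 months", then every 12 weeks. It adds: "This follow-up should be done even if patients start subsequent antineoplastic therapies".

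**Endpoints that do stop at new therapy.** PFS (sections 10.3.1 and 10.4.2) is censored at the last evaluable assessment before further antineoplastic therapy. Section 10.3.2 treats duration of response the same way: "DoR will be censored at the date of the last evaluable tumor assessment before the cut-off or start of further antineoplastic therapy". Section 10.4.2 repeats the trigger for DoR but gives the censoring date only as the last evaluable assessment, without saying that it must precede the new therapy.

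**The concern.** Section 4.3.2 lets patients leave study treatment without RECIST progression because of an adverse event, clinical deterioration, physician decision or their own request. Such a patient may start chemotherapy or another agent and go on being scanned. If the tumour then shrinks, the response falls inside the stated window and is credited to TG4001 plus avelumab, or to avelumab alone.

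Part 2 is open-label, so the decision to switch without RECIST progression could differ between arms. The between-arm ORR comparison could then be biased in either direction. The same patient would be censored for PFS at the last scan before the switch and counted as a responder afterwards, so the plan's own endpoints would disagree about that patient.

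**Working it through.** **1. The plan's own ORR figure.** The only design figure resting on ORR is the part 1 Simon design (section 10.2): at least 3/22, then at least 8/40, with 10% against 25%. The exact two-stage binomial sum, P(at least 3 of 22 and at least 8 of 40), gives 0.0398 at 10% and 0.8032 at 25%. This agrees with the stated 5% and 80%. Nothing in it depends on the response window, so the point is settled by setting the definitions side by side.

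**2. Where each quantity stops.**

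| Quantity | Place | Stops at progression | Stops at further therapy |
|---|---|---|---|
| Best overall response | Appendix IV 3.5 | Yes | No |
| Best response, part 1 | 10.3.1 | Yes | No |
| Efficacy observation, part 2 | 8 | Yes (or death) | No |
| Confirmation of CR/PR | Appendix IV 3.5 | Both scans before it | Not mentioned |
| PFS | 10.3.1, 10.4.2 | Event | Yes, last assessment before it |
| DoR | 10.3.2 | Event | Yes, last assessment before it |
| DoR | 10.4.2 | Event | Trigger yes; date not tied to before it |

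**3. One assumed patient on the 6-week scan grid.** The Day 85 scan shows SD and treatment stops for an adverse event. New therapy starts on Day 100. PR is seen on Day 127 and confirmed on Day 169.
- PFS: censored at Day 85.
- Best overall response: PR, so a responder in ORR.
- DCR: unchanged. SD at Day 85, after more than 5 weeks' exposure, already counts as disease control.
- DoR under 10.3.2: starts Day 127, censored Day 85; 85 − 127 = −42 days.
- DoR under 10.4.2 read literally: starts Day 127, censored at the last evaluable scan. If that is Day 169, 169 − 127 = +42 days.

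**4. Size per patient.** Sections 3.1.2 and 3.2 give at least 80 patients, with a re-estimated target of 120, in the cohort without liver metastases. That is 40 to 60 per arm.
- 1/40 = 2.5 points; 1/60 = 1.7 points.
- For the pooled earlier data (section 1.3.8), one more responder would move 8/34 = 23.5% to 9/34 = 26.5%.

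**5. Range under assumption.** The documents do not give the share of patients who switch without RECIST progression. Let the true response rate be 10%, let a fraction f of non-responders switch in this way, and let a fraction r of those respond on the next therapy. The apparent rate is 0.10 + 0.90 × f × r.
- f = 5%, r = 10%: 0.10 + 0.0045 = 10.5%.
- f = 20%, r = 30%: 0.10 + 0.054 = 15.4%.

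Both f and r are assumptions chosen only to show scale.

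**The case against.** **The exposed group is narrow.** A patient must stop without RECIST progression, start another therapy, and then have a confirmed CR or PR with no progression in between. Responses after RECIST progression are already excluded. For clinical deterioration, sections 4.3.2 and 8 ask sites to make every effort to document objective progression, and documented progression closes the window. The per-protocol set also drops patients below 6 TG4001 and 3 avelumab administrations unless they progressed or died, which removes many early switchers. All of this stands and limits the likely number. It does not close the gap: stops for toxicity or at the patient's request remain, and the full analysis set has no such exposure rule.

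**The SAP may contain the rule.** The protocol refers to an SAP for the adaptive method, laboratory shift tables and protocol deviations. No visible text sends the response window there. A cut stated only in the SAP would still conflict with Appendix IV, so the protocol wording would need aligning in any case.

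**Palliative radiotherapy is handled.** Section 6.3.2 has patients who receive it analysed separately. That does not cover systemic therapy.

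**The confirmation requirement is partly a choice.** Requiring the confirmatory scan before the switch discards a PR first seen on study treatment and confirmed only afterwards. This is a real cost and should be stated.

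**Conclusion.** The gap is real. Followed exactly, the stated rule counts a response to post-study therapy in ORR, and no visible text repairs it. The effect per affected patient is 1.7 to 2.5 points of an arm's ORR at 60 to 40 per arm. The total cannot be estimated because the number of switchers is not given, and it may be small.

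Four stronger readings are tempting but not supported:
- **That DCR is distorted alongside ORR.** It moves only for a patient with no qualifying SD, PR or CR before the switch. The worked patient does not change it.
- **That DoR necessarily takes impossible values.** The negative value follows from section 10.3.2. Section 10.4.2, read literally, need not give it. What is established is that the two texts conflict.
- **That two such patients would account for over a third of the expected ORR gain.** At 40 per arm, two patients are 5 points, and 5/(23.5 − 10) = 37%. But this sets avelumab alone in anal cancer against a pooled single-arm group that includes oropharyngeal cancer and 11 patients with liver metastases. Using the 34.8% seen without liver metastases gives 5/(34.8 − 10) = 20%. Both contrasts are across trials, and the two patients are assumed to fall in one arm only.
- **That the trial's main conclusion is at risk.** Part 2 rests on PFS, which is cut at new therapy. In part 1, where ORR is primary, the second stage was not done. Nothing shows that any reported responder was of this kind.

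**What to change.** In sections 10.3.1 and 10.4.2 and in Appendix IV section 3.5, define best overall response for ORR and DCR on assessments from randomisation (first dose in phase Ib and part 1) up to the earlier of RECIST progression and the start of further antineoplastic therapy. Require both the first and the confirmatory scan of a CR or PR to precede that therapy. Make the section 8 observation window consistent with this. Align the DoR censoring date in section 10.4.2 with section 10.3.2, so that both name the last evaluable assessment before further therapy.

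The cost is a few lines of text and one programming condition. Start dates of further therapy are already recorded (sections 6.10 and 7.7), and the scan schedule need not change. The downside is that ORR may be slightly lower, including loss of a PR first seen on study treatment but confirmed only after a switch. If the sponsor wants to see those patients, they can be listed or counted in a sensitivity analysis.
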